The Big Health team will send the research team information on the number and date of completed Sleepio sessions for each participant (linked to their access code) as well as completed sleep diaries during the treatment. This information will be sent in an encrypted, password-protected spreadsheet and will not include any personally identifiable information. This will be made clear to participants in the PIS.

Data sharing

For increased reproducibility we aim to publish a fully anonymised data set in an open repository after the study has been completed and main results reported. We will make this clear in the PIS and ask participants to consent to this use of their research data.

Statistical analysis

In accordance with Consolidated Standards of Reporting Trials (CONSORT) guidelines, we will record and report all participant flow (Moher 2010) in addition to providing descriptive statistics of recruitment, dropout, and completeness of interventions. The main efficacy analysis will be conducted on an intentionto-treat basis including all participants. Baseline characteristics will be presented by randomization. We will then test the hypothesis for between-group change in the primary and secondary outcomes at 5 weeks and 10 weeks using analysis of covariance with baseline outcome measure and treatment assignment as fixed effects, and apply standard regression diagnostics. The analysis will use statistical techniques for handling missing outcome data under a missing-at random assumption. If the efficacy analysis shows significant between-group differences in the subjective and objective emotion processing measures at 5 and 10 weeks, modern causal inference methods will be to investigate the mediation hypotheses. Parametric regression models will be employed to test for the indirect effect of emotion regulation/processing at week 5 on depression severity (PHQ-9) at 10 weeks. Since all the measures are continuous, the indirect effects are calculated by multiplying relevant pathways and bootstrapping is used to produce valid standard errors for the indirect effects. All analyses will adjust for baseline measures of the mediators, outcomes and putative measured confounders. Mediation analyses are potentially biased by measurement error in mediators and hidden confounding between mediators and outcomes and we will investigate the sensitivity of the estimates to these problems.

Dissemination

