- Serious physical health concerns necessitating surgery or with a survival prognosis of < 6 months
- Habitual night shift, evening, or rotating shift-workers (assessed during last month)
- Suicidal thoughts (Score >1 "yes" on C-SSRS suicide item 2), history of recent suicide attempt (<12 months)
- Psychiatric hospital admission in the past year, or crisis team support within the past year.
- Alcohol misuse & dependency or recreational/illicit drug use

Measurements

The primary and secondary outcome measures are collected at baseline, at 5 weeks and at 10 weeks. The 5 weeks assessment expires after 5 weeks (i.e. at the time of the last assessment) and the 10 weeks assessment expires 4 weeks after the scheduled date, and after the assessments expire participants are no longer able to complete the assessment. The following table lists the variables collected during the trial:

Type of	Measure	Pre-	Baseline	Mid-	Post-
variable		Study	(Week 0)	Treatment (Week 5)	Treatment (Week 10)
	Online Eligibility Screen	Х			
	Demographics		Х		
Primary	FERT		Х	Х	Х
outcome					
and					
mediator					
Secondary	Self-report Emotion		X	X	X
outcome	Regulation: DERS,				
and	PSWQ, PTQ				
mediator					
Secondary	Mood instability		X	X	X
outcome					
Secondary	ISI		X	X	X
outcome					
Secondary	PSQI (4 items)		Χ	X	Χ
outcome					
Secondary	Depression (PHQ-9)		X	X	X
outcome					
Secondary	Chronotype		Х	X	X
outcome					
and					
mediator	Danisius and		V		V
Secondary	Positive and		X	X	X
Outcome and	Negative Affect				
mediator					
Secondary	ECAT		X	X	X
outcome	EGAT		^	^	^
and					
mediator					
Secondary	EMEM		Χ	X	Χ
outcome			^		
and					
mediator					
Auditory	Audit of engagement			Х	Х
variable	with mental health				
	services and sleep				
	medication				
Auditory	Device Monitoring		Х	Х	Х
variable	Question(s)				

Randomisation and allocation concealment

Randomization will be performed independently from the study team through the ePRO system. This study will use stratified randomisation with an allocation ratio of 1:1. Randomisation and stratification according to sex (male/female), age (25-44, 45-65), depression severity (PHQ-9 Scores: $\leq 15: \geq 16$) and insomnia severity (ISI scores $\leq 19: \geq 20$). On completion of baseline measures each participant will be randomly assigned to either dCBT-I or SHE. The team will be unable to influence randomization in the ePRO system, but will manually contact the participant to inform them of their allocation.

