The main efficacy analysis will be conducted on a modified intention-to-treat basis including all participants having at least one outcome. The primary analyses (emotional processing of faces) differences between treatment groups (dCBT-I and SHE), will be estimated with mixed linear regression models. The main objective of the statistical analyses is to assess the effect of dCBT-I on the primary outcome at the end of the intervention period, 10 weeks. To this end a linear mixed modelling will be employed. In such models, the continuous outcome variable measured at the post randomisation time points features as the dependent, the baseline value of the outcome, stratification factors (sex, age, depression severity and insomnia severity), treatment arm (dCBT-I or SHE), assessment time (5 or 10 weeks) and a treatment x time interaction term included as covariates. To account for correlation between repeated measures on the same individual a subject-varying random intercept will be included. Time will be considered as a categorical variable and model fitted assessed for inclusion of a random slope. Model assumptions will be checked using diagnostic plots. Modelling will be based on the assumption that data are missing at random and will be fitted using restricted maximum likelihood estimation. Results from all analyses will be summarised at 5 and 10 weeks with 2 sided 97.5 % CIs and we will present the data from both adjusted (including stratification variables) and unadjusted models. The adjusted model will be considered the primary analysis.

Handling missing data

The analysis will use statistical techniques for handling missing outcome data under a missing-at random assumption (MAR). The availability of the outcome data for the primary outcome at 10 weeks will be summarised by randomised group.

The mixed effects model implicitly accounts for data missing at random, however the data missingness mechanism will be explored. Logistic regression models will explore any association between baseline characteristics and availability of the primary outcome at 10 weeks. Missing primary outcome data will be reported overall and by randomised group. Covariates found to be predictive of missingness (P< 0.05) will be included in the analysis model in a sensitivity analysis of the primary outcome.

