Change in level of morningness (MSF SC from MCTQ)

Change in mood (PANAS-SF, positive and negative affect)

If the efficacy analysis shows significant between-group differences in these measures at 5 and 10 weeks, modern causal inference methods will be used to investigate the mediation hypotheses. Parametric regression models will be employed to test for the indirect effect of emotion regulation/processing/morningness/mood at week 5 on depression severity (PHQ-9) at 10 weeks. Since all the measures are continuous, the indirect effects are calculated by multiplying relevant pathways and bootstrapping is used to produce valid standard errors for the indirect effects. Results will be presented as indirect effects with 95% bootstrapped percentile CIs and also as percentage of the total effect that is mediated. All analyses will adjust for baseline measures of the mediators. An adjusted model, including the stratification variables will also be presented. Mediation analyses are potentially biased by measurement error in mediators and hidden confounding between mediators and outcomes and we will investigate the sensitivity of the estimates to these problems.

CACE analysis

A complier-average causal effect (CACE) analysis of the primary outcome will be carried out to determine what effect the level of compliance to the intervention has on the treatment effect i.e. an estimate of the treatment effect amongst compliant patients. Descriptive statistics will be presented for the primary outcome in the control group, and in the intervention group split by the number of Sleepio sessions attended (i.e. 0,1,2,3, 4, 5, 6).

Baseline characteristic of the participants by compliance status will be reported. Statistical testing of baseline characteristics with compliance will be carried out to determine factors associated with compliance. A table of baseline characteristics by control, complier and non-complier with statistical comparison between compliers and non-compliers in the CBT-I intervention arm will be reported.

To obtain an unbiased estimate of the effect of compliance to the intervention on treatment effect, we will produce the complier-average causal effect estimates of the difference between the mean accuracy scores for sad and happy faces (FERT) for the compliers in the Sleepio group compared to the would be

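### The SAP's mediation models leave out continuous baseline PHQ-9, contrary to the protocol, and both documents gate mediation on significance at week 10 although the mediator is the week-5 value

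*Combined protocol and SAP*

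**What the plan says.** The protocol (Statistical analysis) sets the covariates for mediation: "All analyses will adjust for baseline measures of the mediators, outcomes and putative measured confounders". It does not list the confounders.

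The SAP (Mediation analysis) is narrower. It states: "All analyses will adjust for baseline measures of the mediators. An adjusted model, including the stratification variables will also be presented". It does not say which of the two models is primary. The stratification variables are given under the SAP's primary analysis as "stratification factors (sex, age, depression severity and insomnia severity"); the SAP's randomisation section splits PHQ-9 into 15 or below and 16 or above. Neither mediation model names baseline PHQ-9 as a continuous covariate. By contrast, the PHQ-9 efficacy model (SAP, Secondary outcomes) does include the baseline value of the outcome.

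Mediation is conditional in both documents. The SAP's condition is "If the efficacy analysis shows significant between-group differences in these measures at 5 and 10 weeks"; the protocol's is "significant between-group differences in the subjective and objective emotion processing measures at 5 and 10 weeks". In both, the hypothesised mediator is the week-5 measure and the outcome is PHQ-9 at week 10. Both also promise to examine sensitivity to hidden confounding and to measurement error in the mediator, without naming a method.

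**The concern.** Randomisation protects the treatment-to-mediator path but not the mediator-to-PHQ-9 path. People with higher baseline PHQ-9 will tend to have higher PHQ-9 at week 10. If they also have worse week-5 worry, perseverative thinking, emotion regulation or affect than their own baseline on that measure predicts, mediator and outcome are associated without any causal link. Multiplied by a real treatment effect on the mediator, that association appears as an indirect effect.

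The gate is a separate matter. The week-10 value of the mediator is not part of the stated indirect effect, so requiring significance there can block the test of an early mediator whose group difference narrows. Selecting on significance also overstates the effects that get through.

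Mediation of the effect on depression is the trial's second stated aim and covers SAP hypotheses 7, 8, 9, 12 and 13.

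**Working it through.** **Step 1. The plan's own power figures.** The mediation section gives no figure, but the gate reuses the efficacy tests. 200 randomised less 15% leaves 170, or 85 per arm. In SD units, SE = √(2/85) = 0.1534 and 0.5/0.1534 = 3.260.
- α = 0.05: Φ(3.260 − 1.960) = 0.903, against 90% stated.
- α = 0.025: Φ(3.260 − 2.241) = 0.846, against 85% stated.

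Both reproduce.

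**Step 2. Size of the bias.** Let c be the effect of baseline PHQ-9 on the week-5 mediator, given the baseline mediator. With the true mediator-to-PHQ-9 effect at zero, a model holding only the baseline mediator estimates that path as

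bias = β·c·(1 − ρ²)/(1 − r²).

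Assumed, since the documents do not give them: β = 0.5 (baseline PHQ-9 to week-10 PHQ-9), ρ = 0.5 (baseline mediator with baseline PHQ-9), r = 0.6 (mediator, week 0 with week 5). Then bias = 0.5 × c × 0.75/0.64 = 0.586c. With a 0.5 SD treatment effect on the mediator and the protocol's 0.48 SD effect on PHQ-9 as the total effect, the apparent proportion mediated is 0.5 × 0.586c/0.48 = 0.61c. That is 6%, 12% and 18% at c = 0.1, 0.2 and 0.3, where the truth is zero.

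**Step 3. False-mediation rates.** The setting of step 2 was simulated: n = 170, 3,000 trials per row, nominal 5%, PHQ-9 stratum as a median split. Each cell gives the rate of declared mediation, with the apparent proportion mediated in brackets.

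| c | Baseline mediator only | Plus PHQ-9 stratum | Plus continuous PHQ-9 |
|---|---|---|---|
| 0 | 4.0% (0) | 3.8% (0) | 3.9% (0) |
| 0.1 | 9.9% (6%) | 5.7% (3%) | 4.3% (0) |
| 0.2 | 25% (12%) | 10% (5.5%) | 4.7% (0) |
| 0.3 | 49% (19%) | 16% (9%) | 5.5% (0) |

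With a smaller treatment effect on the mediator, 0.4 SD, the ranges over c = 0.1 to 0.3 are 9–43%, 6–14% and 4–5%. Runs with somewhat different settings reach 49% at the upper end of the first range, so these figures are good to several points only.

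Two boundary cases:
- c = 0 but baseline-mediator reliability 0.70: 11.6%, 6.7% and 4.3%. At 0.87, the protocol's test-retest value for the DERS total: 6.4%, 5.2% and 4.8%.
- No treatment effect on the mediator (c = 0.3): 1.8%, 0.3% and 0.1%. The bias in the second path then has nothing to multiply.

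**Step 4. The gate.** Take true differences of 0.5 SD at week 5 and 0.3 SD at week 10, 85 per arm, two-sided 0.05. The SAP states no alpha for the gate.
- Without baseline adjustment (SE 0.1534): week 5 passes with Φ(1.300) = 0.90; week 10 with Φ(0.3/0.1534 − 1.960) = Φ(−0.004) = 0.50.
- With the baseline adjustment that the SAP specifies, at an assumed baseline correlation of 0.5: SE = 0.1534 × √0.75 = 0.1328. Week 5 passes with Φ(3.764 − 1.960) = 0.96; week 10 with Φ(2.258 − 1.960) = 0.62.

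The chance of passing both cannot exceed the smaller of each pair. Simulated with correlated weeks (0.6 within person in the unadjusted case), it is about 0.48 and 0.61. Among trials that pass, the mean week-5 effect is about 16% and 9% too large.

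The scenario matters. With 0.5 SD at both weeks (between-week correlation of the estimates assumed 0.5; baseline correlation 0 or 0.6), 84% to 97% of trials pass and the inflation is 7% to 1%. With 0.5 SD fading to 0.2 SD, 25% to 37% pass.

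**The case against.** A reader might infer that the SAP's main mediation model discards baseline PHQ-9 and all confounders, and so creates spurious mediation. The documents do not support that.

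- The SAP ranks neither model. Its only ranking, for the efficacy analysis, makes the model with stratification variables primary. By analogy, the milder middle column of step 3 may be the relevant one.
- That model does carry PHQ-9 category, insomnia-severity category, sex and age, and the PHQ-9 stratum alone removes over half of the bias (12% apparent mediation down to 5.5% at c = 0.2). The protocol names no confounder, so none can be shown to have been dropped by name; baseline ISI is not in its wording.
- The bias needs c above zero, or a poorly measured baseline mediator, and a real treatment effect on the mediator. No document gives c. One set of correlations cannot describe DERS, FERT accuracy, ECAT reaction time and sleep midpoint alike, and the entry threshold of PHQ-9 at 10 or above narrows the baseline range.
- The gate is in the protocol too, so it is no SAP departure. It limits how many mediators are tested, and it can also screen out some false mediation: at c = 0.2, with the mediator difference narrowing from 0.4 to 0.25 SD, the rates fall from 21% and 8% to 12% and 4% (baseline mediator only; plus stratum). If the difference is sustained, they barely move.

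All of this stands as limits on size and wording. It does not answer the omission itself. The promised sensitivity work concerns hidden confounding, with no method named; baseline PHQ-9 is measured before randomisation and can simply be adjusted for.

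**Conclusion.** The point holds in a limited form. The two documents disagree on the mediation covariates, and the SAP's narrower set leaves a measured potential confounder of a non-randomised path out of one model and only coarsely represented in the other. The direction is sound whenever c is above zero and treatment moves the mediator. The sizes rest on assumed correlations, and at c = 0 with a well-measured baseline mediator nothing is lost.

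The gate is a lesser design weakness shared by both documents. It matters for effects that fade by week 10 or are weak, and little for a sustained 0.5 SD effect. It is also unclear whether it applies to each measure separately and at what alpha.

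Severity: should-fix. Mediation is secondary and conditional, and the primary FERT comparison, its alpha and the sample size are untouched.

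**What to change.** In the SAP's mediation section, include continuous baseline PHQ-9, the baseline mediator and the stratification factors in both the mediator model and the outcome model, and name this as the primary mediation analysis. State which other measured confounders, if any, are meant by the protocol's phrase. Keep the sensitivity analysis as an addition and name its method.

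If the gate is kept, base it on the week-5 group difference only, say that it applies mediator by mediator, and give its alpha. A week-5 gate still selects on significance: for a 0.5 SD effect the remaining inflation is about 1% to 6%. Removing the gate altogether would avoid that, but it is a trade-off, since more mediators would be tested with no multiplicity control in place.

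The cost is about one extra degree of freedom, SAP wording, and a few more mediator models to run. No new data are needed.

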- 13. Change in mood (PANAS-SF: PA and NA) at week 5 will mediate change in depressive symptoms (PHQ-9) at week 10

Method

Study design

The study is a parallel-group, superiority RCT of digital Cognitive Behavioural Therapy for Insomnia (dCBT-I) versus Sleep Hygiene Education (SHE) control. The study is carried out online and through phone contact with the study team. Participants are screened and provide informed consent online.

Assessments (tasks and questionnaires), allocation to condition, and intervention is carried out through web-based platforms. Online outcome assessment of our primary and secondary dependent variables take place at 0 (baseline), 5 weeks post-randomisation (mid-treatment) and 10 weeks post-randomisation (post-treatment). At week 10 all participants allocated to the SHE are offered dCBT-I to improve their insomnia. Participants are scheduled for a phone call before the baseline assessment to go

through the study procedures, and 2 weeks post randomization to ensure that they have accessed the treatments.

Inclusion/exclusion

We will recruit circa 200 community participants who report clinically-significant insomnia and depressive symptoms. Our inclusion criteria comprise of:

- A positive screen for probable DSM-5 insomnia disorder using items from the Sleep Condition Indicator (SCI) (scoring ≤ 2 on item 1 (sleep latency) or item 2 (wakefulness during the night) + scoring ≤ 2 on item 3 (frequency of disturbance) + scoring ≤ 1 on item 4 (sleep quality) + scoring ≤ 2 on daytime functioning items 5 or 6+scoring ≤ 2 on item 8 (chronicity of problem))
- Endorsement of depressive symptoms in the probable "caseness" range (PHQ score ≥10)
- Aged 25-65 years
- Access to a laptop or desktop computer and a phone and reliable internet access either at home or work
- Being able to read and understand English
- Currently living in the UK.

We will screen for comorbid conditions and medication use via an online survey and exclude people according to the following criteria:

- Engaged in psychotherapy for insomnia or depression
- Previous participation in online (or face to face) sleep treatments
- Hypnotic, psychotropic, or antiepileptic medications
- Psychiatric comorbidities: Psychosis or Bipolar Disorder
- Diagnosis of epilepsy or other neurological disorder
- Diagnoses of mild cognitive impairment or dementia.
- Symptoms of a probable additional sleep disorder (e.g. possible obstructive sleep apnea, restless legs syndrome)

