compliers in the control group (CACE). For the primary CACE analysis, a sufficient level of adherence will be defined as completing at least 3 Sleepio sessions. The analysis will be performed using a two stage residual inclusion regression with randomisation as an IV. In the first stage, a regression of treatment receipt on randomisation will be conducted. In the second stage, a regression of the outcome on treatment receipt will be conducted, adjusting for the first-stage residual as covariates, as well as the same covariates as the intention-to-treat analysis. Bootstrapping will be used to obtain CI due to the two stage approach.

Exploratory analysis

Exploratory analyses will be conducted to assess the effect of dCBT-I on other expressions in the FERT (fear, anger, disgust, surprise, neutral), including the grouping of positive (happy, surprise) vs negative (fear, anger, disgust) expressions. We will also report and conduct exploratory analyses on reaction times and emotion misclassifications from the FERT. Emotion Misclassification is defined as the percentage of misclassifications for each emotion (Number of responses to each emotion when that emotion not displayed/Number of faces of all other expressions). Emotion reaction time is the calculated mean reaction time for correct responses for each emotion (if no correct responses, recorded as a missing value).

For the secondary objective tasks (ECAT, EMEM), we will further report and analyse % accuracy and % of misses (ECAT) and misclassifications of each condition (positive or negative words) and mean reaction time for correct responses for each condition (positive and negative words) (EMEM).

We will report sleep diary data collected as part of the dCBT-I treatment (in the intervention group) and also report % of participants scoring < 11 on the ISI and < 10 on the PHQ-9 after treatment, to provide a clinical context.

Possible predictors of treatment effects on the FERT will be analysed and reported. Specifically, we will investigate early/late chronotype, self-rated emotion regulation, high vs low depression scores (PHQ-9 dichotomised at 15) and worry as predictors of responses. Moderators will be assessed separately by repeating the primary analysis model and including an interaction term between randomised treatment and the moderator.

Sensitivity analysis

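### SAP, CACE analysis: the second stage inherits an ITT covariate list that names treatment arm, which contradicts randomisation as the instrument and leaves the complier effect unidentified as written

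*Combined protocol and SAP*

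**What the plan says.** The SAP section on CACE analysis sets out the method: "The analysis will be performed using a two stage residual inclusion regression with randomisation as an IV". Receipt is binary: "a sufficient level of adherence will be defined as completing at least 3 Sleepio sessions". The target is the difference in mean sad and happy accuracy "for the compliers in the Sleepio group compared to the would be" compliers in the control arm.

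The stages are then described. "In the first stage, a regression of treatment receipt on randomisation will be conducted"; no covariates are named for it. The second stage regresses the outcome on receipt, "adjusting for the first-stage residual as covariates, as well as the same covariates as the intention-to-treat analysis".

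The ITT covariates are listed in the SAP under Primary analysis, Primary outcome. The list opens with "the baseline value of the outcome, stratification factors (sex, age, depression severity and insomnia severity") and continues with "treatment arm (dCBT-I or SHE), assessment time (5 or 10 weeks) and a treatment x time interaction term included as covariates".

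No section says which of these terms carry over to the CACE model. The CACE text also names no visit, although it declares the analysis for the primary outcome, which the SAP places at 10 weeks.

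**The concern.** An instrument has to be left out of the outcome equation. That exclusion is what lets the arm difference be attributed to receipt. The SAP calls randomisation the instrument and, by reference, also puts it back into the outcome equation as a covariate. Both instructions cannot be followed.

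The conflict goes beyond style. With arm in the second stage there is no unique receipt coefficient, and what is reported depends on which redundant column the software removes. One of the possible answers is the comparison of completers with non-completers that a CACE analysis exists to avoid.

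The complier estimate is likely to be read closely. The protocol's background section reports that only 33% of the intervention group in the previous study accessed the intervention, and the stop-go pilot phase is built on adherence.

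**Working it through.** **Inputs.** From the SAP: a binary receipt D; arm Z (1 = dCBT-I); a first stage of D on Z; and the two covariate lists above. From the SAP sample size section: 200 participants with 15% attrition, so 200 x 0.85 / 2 = 85 per arm. The documents give no figure for the CACE model, so there is none to reproduce. As a check on the 85 per arm, power at a standardised effect of 0.5 is 84.6% at alpha 0.025 (stated 85%) and 90.3% at alpha 0.05 (stated 90%).

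**Step 1: the collinearity.** The linear first stage gives, exactly,

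D = a + bZ + r, where r is the residual.

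SHE participants are not offered Sleepio earlier ("At week 10 all participants allocated to the SHE are offered dCBT-I to improve their insomnia"), so a = 0 and b = p, the share of the dCBT-I arm with at least 3 sessions. The dependence itself holds for any a. Write the second stage as

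Y = c0 + c1 D + c2 r + c3 Z + covariates.

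Substituting D = pZ + r gives

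Y = c0 + (c1 + c2) r + (c3 + p c1) Z + covariates.

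The data determine two quantities, c1 + c2 and c3 + p c1, but there are three coefficients.
- Drop arm (c3 = 0): c1 is the arm coefficient divided by p, the intended instrumental-variable estimate.
- Drop the residual (c2 = 0): c1 is the coefficient of r given arm, the difference between completers and non-completers within the dCBT-I arm.

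Rank confirms this. The columns {1, D, r, baseline, Z} have rank 4 of 5. With both visits, time and arm x time added, the rank is 6 of 7. Adding baseline to a linear first stage leaves it at 4 of 5. A logistic first stage on arm alone gives the same response residuals (largest difference about 3e-9). A logistic first stage with covariates would break the exact dependence, but the SAP names no first-stage covariates.

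**Step 2: the visit.** Keep both visits and arm x time (coefficient c4), and drop arm. The arm difference is p c1 at week 5 and p c1 + c4 at week 10. So c1 is the week-5 complier effect; the week-10 effect would be c1 + c4/p. If arm x time is removed as well but both visits stay, receipt has one coefficient for two visits. With equal numbers at each visit and effects of 0.25 and 0.5, that is (0.25 + 0.5)/2 = 0.375.

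**Step 3: simulation.** N = 200. These inputs are assumptions, not document figures: compliers differ from never-takers by 0.5 outcome units without treatment; the true complier effect is 0.25 at week 5 and 0.5 at week 10. There were 1,000 trials per row (300 for the last column). Entries are mean receipt coefficients.

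| Compliance | Week 10, arm omitted | Week 10, residual dropped | Both visits, arm dropped, arm x time kept |
|---|---|---|---|
| 33% | 0.478 | 0.992 | 0.263 |
| 50% | 0.489 | 0.986 | 0.244 |
| 66% | 0.487 | 0.996 | 0.230 |
| 80% | 0.501 | 0.988 | 0.237 |

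With a true effect of 0, at 33%, 66% and 80% compliance, omitting arm gave -0.018, 0.005 and -0.003. Dropping the residual gave 0.493, 0.498 and 0.490. The bias equals the assumed selection difference: 0.5 + 0.5 = 1.0 in the first case, 0 + 0.5 = 0.5 in the second.

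On a points scale, assume 85 per arm, 60% compliers and an SD of about 10. With no true effect, the residual-dropped fit gave 3.2 to 3.3 points if unmeasured motivation correlates 0.2 with the outcome, and 6.4 to 6.5 at 0.4. With a true effect of 5 it gave 8.2 and 11.4, against 4.9 to 5.1 with arm omitted.

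**Step 4: what R does.** One simulated data set with no true effect was used. In `lm`, entering receipt and residual first dropped arm (receipt coefficient -0.088); entering the ITT covariates first dropped the residual (0.518). In `lme4::lmer` with both visits, the same two orders gave -0.200 and 0.448, each with a rank-deficiency message. `nlme::lme` stopped with a singularity error.

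**The case against.** The strongest reply is that the harmful reading goes against the surrounding text. The section calls randomisation the instrument and makes receipt the exposure. The primary analysis section uses the word adjusted for models with the stratification variables, and its unadjusted model must still contain arm, so arm is the effect being estimated and not an adjuster. On that reading the inherited covariates are baseline FERT and the stratification factors, and the model is sound. Most analysts who honour the instrument statement would reach it. This stands as a limit on likelihood. It does not remove the contradiction, because the SAP's own list expressly calls arm and the interaction covariates.

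Second, the CACE sentence lists receipt and residual before the ITT covariates, and in that order R's `lm` and `lmer` drop arm. That gives the correct answer for a week-10 model. With both visits and arm x time kept, the same order returns the week-5 effect.

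Third, the SAP elsewhere places the primary hypothesis and main objective at 10 weeks and makes week-5 FERT accuracy secondary, so a week-10 outcome can be inferred. That is fair. But the inherited list contains time and arm x time, which have no place in a week-10 model, so the inference again requires setting part of the list aside.

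Fourth, the SAP's statistical software section names eefAnalytics for the CACE analysis. That package was not tested, and the documents do not say how it treats these terms. The `lm`, `lmer` and `lme` results show what can happen, not what the planned run will do.

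**Conclusion.** The point holds as a contradiction in the SAP. Taken literally, the second stage is exactly collinear and does not identify the complier effect. This follows from algebra and needs no assumption about the data. Depending on term order and package, the fit may fail, be correct, return the within-arm contrast, or return the week-5 effect.

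A reader might infer that the trial will report a confounded complier effect of some 3 to 6 points. The documents do not support that. It would take a reading against the instrument statement, a particular column order and a disregarded software message, and the size rests on assumed selection, compliance and SD. A reader might also infer that low uptake ended the previous study. The protocol says only that the study was performed, that uptake was low and that its outcome data were hard to interpret.

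The primary ITT result is unaffected. This is a supplementary analysis, but the SAP presents its estimate as unbiased, so the wording should be corrected before the analysis is run.

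**What to change.** Replace the covariate clause in the SAP's CACE section with an explicit model, for sad and happy accuracy in turn:

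> Second stage: week-10 FERT accuracy on receipt (at least 3 Sleepio sessions), the first-stage residual, baseline FERT accuracy and the four stratification factors (sex, age, depression severity, insomnia severity). Arm, time and arm x time are excluded. Bootstrap confidence intervals are obtained by repeating both stages in each resample.

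Using the same baseline covariates in the first stage is optional: in simulation the estimator without arm was unbiased with no first-stage covariates. It would also help to confirm that the named package fits this specification.

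The cost is SAP wording only, with no new data, no change to the sample size and no change to the primary analysis.
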